## 4. PLANNED ANALYSES

The following analyses are planned for this study:

- Independent Data Monitoring Committee (IDMC) analyses.
- Interim Analysis.
- Final Analysis.

[figure not shown]
### 4.1. INDEPENDENT DATA MONITORING COMMITTEE (IDMC)

Unblinded IDMC analyses are planned for this study in order to ensure subject safety and monitor tolerability of the investigational vaccine. The IDMC will review safety and reactogenicity data from the current study as well as data from the EBOLA-Z ChAd3-005 study, which will be conducted in parallel with the current study.

Study vaccinations in this study will only start after a favourable outcome of an IDMC review of the safety and reactogenicity data from 100 adults after a 1-week follow-up in the EBOLA-Z ChAd3-005 study. In addition, vaccination at Day 0 will be done in a staggered manner, starting with the children in the oldest age stratum (13 to 17 years). For each age stratum, the IDMC will conduct a review of all available safety data once data is available up to at least 7 days after vaccination of at least 50 subjects, in that age stratum.

In order to proceed to vaccination of the subjects in the younger age stratum (6 to 12 years), a favourable outcome of the IDMC review of safety data up to at least 7 days after vaccination from at least 50 subjects (25 subjects per treatment group) in the oldest age stratum needs to be obtained. The same will be done for moving from the 6 to 12 years age stratum to vaccination of the youngest children (1 to 5 years). Refer to Figure 2: Overview of Staggered Design and Independent Data Monitoring Committee (IDMC) Safety Evaluations below for a description of the staggered approach per age stratum.

Figure 2: Overview of Staggered Design and Independent Data Monitoring Committee (IDMC) Safety Evaluations

\* Safety evaluation on all available safety data from the entire study, which will include the safety data up to 7 days after vaccination at Day 0 from at least 50 subjects (25 subjects/ group) in the respective age stratum.

For the unblinded IDMC analyses the QuintilesIMS Biostatistics blinded team will produce all the required programs and blinded outputs. These programs and outputs will be transferred to the QuintilesIMS Biostatistics unblinded team. The QuintilesIMS Biostatistics unblinded team will reproduce all outputs based on the actual randomisation schedule and will then be responsible for providing the unblinded outputs to the IDMC members as specified in the latest version of the Biostatistics Blinded to Unblinded Team Handover Document (CS\_TP\_BS0214) for the EBO-Z CHAD3-004 study. Refer to the latest version of the unblinding plan for additional details with regard to the handling of unblinded information.

A separate set of IDMC TLF shells (latest version of EBO-Z\_CHAD3\_IDMC\_Shells) has been created specifically for the IDMC analyses. In addition, the IDMC charter can be referenced for additional information regarding the IDMC analyses.

## 4.2. INTERIM ANALYSIS

An unblinded interim analysis will be conducted when safety and immunology data up to Day 30 have been collected for all subjects. All available safety and immunogenicity data in the interim analysis transfer will be included in the interim analysis. As per protocol, the blinded team will be unblinded at the time of the interim analysis and will produce the unblinded interim analysis TLFs.

The cleaning of the 30-day safety data for each subject will be scheduled to be completed prior to the unblinding in order to keep the blind during data cleaning activities.

The interim analysis is planned once the following has been completed:

- GSK's authorization of the following:
  - o SAP. o Relevant TLF shells. o Analysis cohort assignments.
- Immunogenicity data availability:

Document: CHAD3-004-EBO-Z\_Interim\_Final\_SAP\_v2\_0  
 Author: PPD Version Number: 2.0 Version Date: 14JUN2017

Template No: CS\_TP\_BS016 – Revision 3  
 Effective Date: 01May2012

Reference: CS\_WI\_BS005

- o At least the Day 30 anti-GP EBOV data should be available.
- Interim analysis data transfer from Data Management.

The interim analysis data transfer should comply with:

- All the data up to Day 30 is clean:
  - o All outstanding data issues and queries resolved.
  - o All unresolvable data issues documented in the Data Handling Report (DHR), a separate document produced by Data Management.
  - o All coding, for example AEs, is completed. o All reconciliation of vendor data with eSource data completed successfully.
- Any additional data post-Day 30 should be as clean as possible.

### 4.3. FINAL ANALYSIS

All final, planned analyses identified in this SAP and relevant set of TLF shells will be performed by the QuintilesIMS Biostatistics blinded team. The final analysis is planned for when all subjects had completed study participation, following:

- GSK's authorization of the following:
  - o Final version of the SAP. o Relevant set of TLF shells.
  - o Analysis cohort assignments.
- Final database lock.
- All immunology data are available.

The final analysis will be performed on a clean database transfer:

- All outstanding data issues and queries were resolved.
- All unresolvable data issues documented in the DHR, a separate document produced by Data Management.
- All coding, for example AEs, is completed.
- All reconciliation of vendor data with eSource data completed successfully.

## 5. ANALYSIS COHORTS

GSK's authorization of the analysis cohort assignments is required at two time points:

- Prior to the interim analysis: Interim analysis cohort authorization.
- Prior to the final analysis: Final analysis cohort authorization:
  - o Prior to the final analysis there will only be a review of the interim analysis cohort assignments as a confirmation of the inclusion of all subjects in the relevant analysis cohorts.

Refer to the relevant analysis cohort assignment documentation (latest version of CHAD3-004-EBO-Z\_Cohort\_Assignment\_Plan) for additional information.

### 5.1. TOTAL ENROLLED COHORT

The Total Enrolled Cohort is defined as all subjects who signed informed consent, regardless of being randomised to either:

- EBO-Z/MENACWY-TT.
- MENACWY-TT/EBO-Z.

The Total Enrolled Cohort will be programmatically derived based on the informed consent information recorded on the Screening form in eSource.

### 5.2. TOTAL RANDOMISED COHORT

The Total Randomised Cohort is defined as all subjects who were randomised to either EBO-Z/MENACWY-TT or MENACWY-TT/EBO-Z, regardless of whether they received a vaccination.

A subject will be programmatically included in the Total Randomised Cohort if the subject had been randomised based on the treatment allocation information recorded on the Visit Day 0 form in eSource or reported in the Interactive Web Randomisation System (IWRS).

For analyses and presentations based on the Total Randomised Cohort, subjects are to be analysed according to the treatment allocated regardless of the treatment received.

### 5.3. TOTAL VACCINATED COHORT (TVC)

The Total Vaccinated Cohort (TVC) is defined as all subjects included in the Total Randomised Cohort who received at least one vaccination. The TVC is defined separately for safety and immunogenicity analyses as described below:

- Safety Analysis:

---

Document: CHAD3-004-EBO-Z\_Interim\_Final\_SAP\_v2\_0  
Author: PPD Version Number: 2.0 Version Date: 14JUN2017

Template No: CS\_TP\_BS016 – Revision 3  
Effective Date: 01May2012

Reference: CS\_WI\_BS005

- o A subject is to be programmatically included in the TVC if the subject has at least one date of vaccination available in the database.
  - o Labelled as 'Total Vaccinated Cohort' in relevant TLF shells.
- Immunogenicity Analysis:
  - o Immunogenicity analysis based on the TVC will include all vaccinated subjects for whom immunogenicity results are available, however, due to the fact that only subjects with data available are to be included per time point for the immunogenicity analysis, there will be no additional elimination required. The TVC for safety and immunogenicity analyses are defined as the same cohort of subjects.

Subjects who received a different treatment to that allocated are to be analysed as described below:

- Analyse subject according to the treatment received at Day 0 (first vaccination).

## 5.4. ACCORDING-TO-PROTOCOL COHORT (ATP)

The According-to-protocol (ATP) Cohort is defined as all evaluable subjects satisfying the following:

- Meet all eligibility criteria.
- Received at least one dose of study vaccine according to protocol procedures and randomisation.
- Randomisation code has not been broken for vaccination at Day 0.
- Comply with the procedures and intervals defined in the protocol.
- Did not receive a concomitant medication/product/vaccination leading to elimination from an ATP analysis (refer to relevant section in the protocol, Section 6.7.2).
- Did not present with a medical condition leading to elimination from an ATP analysis (refer to the relevant section in the protocol, Section 6.8).
- Data concerning immunogenicity endpoint measurements are available.

The ATP Cohort will be used for immunogenicity analyses and will be defined prior to:

- Planned Interim Analysis based on the elimination code process.

Subjects included in the ATP Cohort did not receive a different treatment to that allocated, therefore the analysis would be the same for subjects whether based on the randomised or allocated treatment.

## 5.5. SUB-COHORTS AND SUBSETS OF SUBJECTS

### 5.5.1. SUB-COHORT FOR CELL-MEDIATED IMMUNITY (CMI)

---

Document: CHAD3-004-EBO-Z\_Interim\_Final\_SAP\_v2\_0  
Author: PPD Version Number: 2.0 Version Date: 14JUN2017

Template No: CS\_TP\_BS016 – Revision 3  
Effective Date: 01May2012

Reference: CS\_WI\_BS005

The first approximately 30 subjects randomised per age stratum and group, (180 subjects in total, 90 per group) will be included in this sub-cohort. Subjects will be included from selected centres (refer to Section 7.2: Multicentre Studies) only. A blood sample for assessment of CMI should be taken from the subjects at the following visits:

- Day 0.
- Day 30.
- Month 6.
- Month 6 + 30 days.
- Month 12.

This sub-cohort will be programmatically assigned based on the relevant treatment allocation information recorded on the Visit Day 0 form in eSource. This sub-cohort will be labelled as the CMI Sub-cohort in the relevant presentations.

#### 5.5.2. SUBSET FOR ADDITIONAL TESTING

A subset of the subjects will have additional humoral immunogenicity assays performed. These will be the same subjects as the subjects in the sub-cohort for CMI. These subjects will have the neutralizing antibodies assays performed. Other subjects will have the same samples available, however these samples will be used for other testing and not analysed within this protocol. This subset will be labelled as the Subset for Additional Testing in the relevant presentations.

## 6. GENERAL CONSIDERATIONS

### 6.1. REFERENCE START DATE AND RELATIVE DAY

Reference start date is defined as the date of first vaccination, and equals the Day 0 date. Relative day is calculated relative to the reference start date and is to be used to show start and stop day of an assessment or event. Relative day is calculated as follows:

- Relative day = (date of assessment/event – reference start date).

Unless otherwise specified, if the date of the assessment/event is partial or missing, relative day and any corresponding durations will not be calculated and will be presented as missing in the listings. Imputed AE dates will be used in order to assign the AEs as either within or outside the relevant collection period and will not be used to calculate an imputed relative day (refer to APPENDIX 2: Partial Date Conventions).

Some presentations might include the relative day relative to the most recent vaccination (refer to Section 6.7.2: Most Recent Vaccination) and will be calculated as follows:

- If the date of the assessment/event is on or after the most recent vaccination:
  - o Relative day to most recent vaccination = (date of event – date of most recent vaccination).

### 6.2. BASELINE

Unless otherwise specified, Baseline is defined as the last non-missing assessment (scheduled or unscheduled) prior to the first vaccination. In the case where the last non-missing assessment and the reference start date coincide, that assessment will be considered pre-baseline (unless specified as post-vaccination). However, adverse events (AEs) starting on the reference start date will be considered post-baseline.

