### 6.3. DERIVED TIME POINTS

#### 6.3.1. CHAd3-EBO-Z POST-VACCINATION TIME POINTS

As a first step, safety and/or immunogenicity results will be presented by treatment administered at Day 0.

In a second step, all available data post-vaccination with the investigational vaccine (Day 0 for the EBOZ/MENACWY-TT and Month 6 for the MENACWY-TT/EBO-Z treatment groups, respectively) will be pooled. All available safety and immunogenicity data following the ChAd3-EBO-Z vaccination in both the treatment groups will be pooled at the time points as specified in Table 2: Derivation of ChAd3-EBO-Z Post-vaccination Time Points:

Table 2: Derivation of ChAd3-EBO-Z Post-vaccination Time Points

---

Document: CHAD3-004-EBO-Z\_Interim\_Final\_SAP\_v2\_0  
Author: PPD Version Number: 2.0 Version Date: 14JUN2017

Template No: CS\_TP\_BS016 – Revision 3  
Effective Date: 01May2012

Reference: CS\_WI\_BS005

ChAd3-EBO-Z Post-vaccination Time Point	Treatment Group	Visit
0 Days Post-vaccination with EBO-Z	EBO-Z/MENACWY-TT	Day 0
	MENACWY-TT/EBO-Z	Month 6
6 Days Post-vaccination with EBO-Z	EBO-Z/MENACWY-TT	Day 6
	MENACWY-TT/EBO-Z	Month 6 + 6 Days
30 Days Post-vaccination with EBO-Z	EBO-Z/MENACWY-TT	Day 30
	MENACWY-TT/EBO-Z	Month 6 + 30 Days
3 Months Post-vaccination with EBO-Z	EBO-Z/MENACWY-TT	Month 3
	MENACWY-TT/EBO-Z	Month 9
6 Months Post-vaccination with EBO-Z	EBO-Z/MENACWY-TT	Month 6
	MENACWY-TT/EBO-Z	Month 12

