## 6.7. COMMON CALCULATIONS

### 6.7.1. CHANGE FROM BASELINE

For quantitative measurements, change from Baseline will be calculated as:

- Change from Baseline at Day x = (Result at Day x – Baseline Result).

If a result/value is missing, the change from Baseline will be presented as missing in the listing; hence no imputation for a missing change from Baseline will be performed.

---

Document: CHAD3-004-EBO-Z\_Interim\_Final\_SAP\_v2\_0

Author: PPD Version Number: 2.0 Version Date: 14JUN2017

Template No: CS\_TP\_BS016 – Revision 3

Reference: CS\_WI\_BS005

Effective Date: 01May2012

Copyright © 2012 Quintiles Transnational Corp. All rights reserved.

The contents of this document are confidential and proprietary to Quintiles Transnational Corp. Unauthorised use, disclosure or reproduction is strictly prohibited.

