- Day 0 Reverse Cumulative Distribution curve:
  - o The plot shows antibody concentrations (on a log-scale) on the X-axis and the proportion of individuals exhibiting that concentrations or higher on the Y-axis.
  - o This output would only contain the Baseline seropositive subjects. o Only Day 0 results will be presented.
- Concentration and GMCs:
  - o Individual antibody concentrations at Day 0 and Day 30, with dot plots, per treatment group. o GMCs and 95% confidence intervals will also be plotted.
- Kinetic plot (only applicable to the final analysis):
  - o GMCs, including 95% CIs at the EBO-Z post-vaccination time points. o Time points will be connected with straight lines.

All anti-GP EBOV tables will be presented by Baseline serological status, including the following categories:

- Seronegative.
- Seropositive.
- Total.

The following immunology variables, as presented in the planned TLF shells, will be collected on the Blood Sampling form in eSource:

- Were humoral immunity blood samples collected:
  - o Y

---

Document: CHAD3-004-EBO-Z\_Interim\_Final\_SAP\_v2\_0

Author: PPD Version Number: 2.0 Version Date: 14JUN2017

Template No: CS\_TP\_BS016 – Revision 3

Reference: CS\_WI\_BS005

Effective Date: 01May2012

es. o

No.

- Date and time of sample collection.

The following immunology variable, as presented in the planned TLF shells, will be imported from the laboratory report:

- Concentration value.

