#### 14.1.2. CHAd3 NEUTRALISING ANTIBODY

All analyses will be the same as described for the anti-GP EBOV data. The same tables as described for the antiGP EBOV data will be prepared for the ChAd3 neutralisation data. The ChAd3 neutralisation result will be the reciprocal antibody titres corresponding to the inhibitory concentration 90% (IC90, the titre at which 90% of infectivity is inhibited).

In addition, the association of the pre-existing (baseline) ChAd3 neutralisation antibodies with each of the following vaccine-induced (Day 30 post-vaccination) results will be evaluated by the Spearman-rank correlation method:

- Anti-GP EBOV: Concentration.
- Frequency of CD4+ T-cell specific to EBOV:
  - o CD4+/IFN. o  
CD4+/I  
L2.
  - o CD4+/TNF.
- Frequency of CD8+ T-cell specific to EBOV:
  - o CD8+/IFN. o  
CD8+/I  
L2. o  
CD8+/T  
NF.

Three scatter plots will be presented per cytokine (IFN, IL2, TNF), one plot for each of the aforementioned sets of results. The vaccine-induced results will be based on the result observed at Day 30. The figure will be repeated for the 30 Days Post-vaccination derived time point as defined in Section 6.3.1: ChAd3-EBO-Z Post-vaccination Time Points.

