### 15.4. LABORATORY EVALUATIONS

Document: CHAD3-004-EBO-Z\_Interim\_Final\_SAP\_v2\_0  
Author: PPD Version Number: 2.0 Version Date: 14JUN2017

Template No: CS\_TP\_BS016 – Revision 3  
Effective Date: 01May2012

Reference: CS\_WI\_BS005

- 

The list of laboratory assessments to be included in the analysis is provided in APPENDIX 5: Laboratory Assessments.

The following listings are planned for presentation based on the Total Randomised Cohort:

- Clinical laboratory results, including change from Baseline and toxicity grading.
- Clinical laboratory results: Platelets, including an indication of subjects with AESIs.
- Malaria rapid diagnosis test (RDT) results.
- Pregnancy test results:
  - o Based on the Total Enrolled Cohort and only includes female subjects with results available.

The following tables are planned for presentation based on the Total Vaccinated Cohort:

- Clinical laboratory results, including change from Baseline:
  - o Descriptive statistics, including the interquartile range.Out of range clinical laboratory results:
  - o Number and percentage (%) of subjects with results above or below the normal range.
  - o Percentage (%) is relative to the number of subjects with result available for the specific test and the relevant time point.
- Toxicity grade shift from Baseline to post-baseline, the table will include the following categories:
  - o Grade 0. o Grade 1. o Grade 2. o Grade 3.
  - o Grade 4.
- Clinical Laboratory Percent Decrease from Baseline to Post-baseline: Platelets ( $10^9/L$ ):
  - o Number and percentage (%) of subjects with decrease in platelets in the derived categories will be summarized.
  - o Decrease in platelets from Baseline will be categorised as follows: Any increase
    - 0 to <10% decrease
    - 10% to <20% decrease
    - $\geq 20\%$  decrease o This table will be repeated for the maximum percent decrease observed between Day 3 and Day 6. o This table will not be repeated as a pooled table.
- Reported pregnancies per most recent vaccination and centre:
  - o The number and percentage (%) of reported pregnancies will be presented per most recent vaccination (Day 0 or Month 6) and centre as well as overall.
  - o The percentage will be based on the number of female subjects of childbearing potential within each centre.

All laboratory tables (unless otherwise noted) will be repeated for the following pooling of results:

---

Document: CHAD3-004-EBO-Z\_Interim\_Final\_SAP\_v2\_0

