Author: PPD Version Number: 2.0 Version Date: 14JUN2017

Template No: CS\_TP\_BS016 – Revision 3

Reference: CS\_WI\_BS005

Effective Date: 01May2012

Copyright © 2012 Quintiles Transnational Corp. All rights reserved.

The contents of this document are confidential and proprietary to Quintiles Transnational Corp. Unauthorised use, disclosure or reproduction is strictly prohibited.

- Results following the active ChAd3-EBO-Z vaccination; hence:
  - o EBO-Z/MENACWY-TT subjects: Laboratory results following Day 0 vaccination.
  - o MENACWY-TT/EBO-Z subjects: Laboratory results following Month 6 vaccination.

The following figure is planned for presentation based on the Total Vaccinated Cohort:

- Platelet: Quartile Distribution following Day 0 Vaccination:
  - o Box and whisker plot presenting the platelet distribution up to Day 30. o The mean, median as well as the Q1 and 3 values will be presented on the figure. o The treatment groups will be presented separately on the same figure.

The following laboratory variables, as presented in the planned TLF shells, will be recorded on the Blood Sampling form in eSource:

- Date and time of sample collection:
  - o Haematology samples.
  - o Biochemistry samples.

The following laboratory variables, as presented in the planned TLF shells, will be recorded on the Laboratory Results form in eSource:

- Date of sample collection:
  - o Haematology samples.
  - o Biochemistry samples.
- Result and unit.
- Significance:
  - o Not clinically significant (NCS).
  - o Clinically significant (CS).

The following laboratory variables, as presented in the planned TLF shells, will be recorded on the Malaria RDT and Results form in eSource:

- Date and time of assessment.
- Result:
  - o Positive.
  - o Negative.
- Malaria treatment prescribed per local/national requirements:
  - o Yes.
  - o No.
- Prescribed malaria treatment completed:

---

Document: CHAD3-004-EBO-Z\_Interim\_Final\_SAP\_v2\_0

Author: PPD Version Number: 2.0 Version Date: 14JUN2017

Template No: CS\_TP\_BS016 – Revision 3

Reference: CS\_WI\_BS005

Effective Date: 01May2012

- - o Yes.
  - o No.

The following laboratory variables, as presented in the planned TLF shells, will be recorded on the Pregnancy Test form in eSource:

- Date and time of assessment.
- Result:
  - o Positive.
  - o Negative.

The following pregnancy variables, as presented in the planned TLF shells, will be recorded on the Pregnancy Report form in eSource:

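### The pooled post-ChAd3-EBO-Z laboratory tables use a Baseline from before the Day 0 vaccination, which is 5 to 8 months old at the ChAd3-EBO-Z dose for children vaccinated at Month 6

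*SAP*

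**What the plan says.** All SAP references are to version 2.0.

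- **Baseline.** Section 6.2 gives a default that holds unless something else is specified: "Baseline is defined as the last non-missing assessment (scheduled or unscheduled) prior to the first vaccination". Section 6.1 fixes the anchor: "Reference start date is defined as the date of first vaccination, and equals the Day 0 date". In Group MENACWY-TT/EBO-Z that first dose is Nimenrix. Section 6.7.1 has a single change-from-Baseline formula and no variant for pooled data.
- **Pooling.** Section 6.3.1 and Table 2 realign the visits, so that Month 6 in Group MENACWY-TT/EBO-Z becomes "0 Days Post-vaccination with EBO-Z". They do not call that visit Baseline.
- **Laboratory tables.** Section 15.4 states: "All laboratory tables (unless otherwise noted) will be repeated for the following pooling of results". For the second group the pool holds "MENACWY-TT/EBO-Z subjects: Laboratory results following Month 6 vaccination". The repeated tables include change from Baseline and the toxicity grade shift. The platelet percent-decrease table is expressly not pooled.
- **Immunogenicity.** Section 14 repeats the immunogenicity tables at the realigned time points. Section 14.1.1 adds: "All anti-GP EBOV tables will be presented by Baseline serological status, including the following categories". Section 14.1.2 evaluates "the association of the pre-existing (baseline) ChAd3 neutralisation antibodies with each of the following vaccine-induced (Day 30 post-vaccination) results" and repeats the figure at the pooled 30-day point. Response and seroconversion (Sections 14.1.1.1 and 14.1.2.1) and the serostatus used for the CMI tables (Section 14.2.1.1) refer only to a pre-vaccination value, without naming the vaccination.

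**The concern.** The pooled step is meant to describe what happens after ChAd3-EBO-Z in all recipients. Its visits are aligned to the ChAd3-EBO-Z dose, but its reference value is aligned to whatever was injected first. For half of the planned recipients those are about six months apart.

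In Group MENACWY-TT/EBO-Z, any laboratory change between Screening and Month 6 (growth, season, intercurrent infection) would be carried into the post-ChAd3-EBO-Z column. Protocol Table 5 schedules the malaria test at Screening only, so nothing resets the child's state before the Month 6 dose. Protocol Section 11.8 says that the pooled data cannot be shown against control. No comparator would reveal the drift, and Baseline is the only reference the reader has.

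On the serology side, a child could sit in a serostatus stratum that no longer applies. The analysis of pre-existing vector immunity could also use a level that is not the one present when the vector was given.

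**Working it through.** **1. Number of children.** SAP Table 1 plans 3 age strata x about 100 = 300 per group, and Protocol Section 11.8 also states 300. The figure is consistent with Protocol Table 22: the exact upper limit for 0 of 300 is 1 − 0.025^(1/300) = 0.0122, as printed.

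**2. Age of the Baseline.** The inputs are the allowed intervals in Protocol Table 6:
- Screening to Day 0: 0 to 30 days.
- Day 0 to Month 6: 6 months ± 30 days.
- Month 6 to Month 6 + 6 days: 6 to 8 days.
- Month 6 to Month 6 + 30 days: 30 to 44 days.
- Month 6 to Month 12: 6 months ± 30 days.

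Six months is taken as 6 x 365.25/12 = 182.6 days. Haematology and biochemistry are sampled at Screening and not again until Day 3 (Protocol Section 3), so the laboratory Baseline is the Screening value. Serology and CMI are sampled at Day 0.

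For Group MENACWY-TT/EBO-Z at the ChAd3-EBO-Z dose:
- Laboratory: minimum 0 + 182.6 − 30 = 152.6 days; maximum 30 + 182.6 + 30 = 242.6 days. That is 153 to 243 days, or 5.0 to 8.0 months.
- Serology and CMI: 182.6 ± 30 = 153 to 213 days, or 5.0 to 7.0 months.

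Taking six months as 180 days gives 150 to 240 and 150 to 210 days.

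Age of the laboratory Baseline at each pooled point:

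| Time since ChAd3-EBO-Z | MENACWY-TT/EBO-Z | EBO-Z/MENACWY-TT |
|---|---|---|
| At the dose | 153 to 243 days (5.0 to 8.0 months) | 0 to 30 days |
| 6 days | 159 to 251 days (5.2 to 8.2 months) | 6 to 38 days |
| 30 days | 183 to 287 days (6.0 to 9.4 months) | 30 to 74 days |
| 6 months | 305 to 455 days (10.0 to 15.0 months) | 153 to 243 days (5.0 to 8.0 months) |

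**3. Effect on a pooled mean change.** Let e be the change after ChAd3-EBO-Z, assumed equal in both groups, and d the change between Screening and Month 6 in Group MENACWY-TT/EBO-Z. Drift within the screening interval is ignored. Then the pooled mean = [300e + 300(d + e)]/600 = e + d/2. The documents give no value for d. The result holds for means with equal group sizes. Protocol Section 11.8 asks for medians and interquartile ranges, for which there is no such simple formula.

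**4. Effect on the toxicity shift.** Here the direction can be read from Protocol Appendix C, because the eligibility limits nearly coincide with the edge of Grade 1:
- Age 12 or under: haemoglobin eligible from 8.5, Grade 1 is 7.5 to 8.49; platelets eligible from 100, Grade 1 is 75 to 99.999; white cells eligible from 4, Grade 1 is 2.5 to 3.999; creatinine eligible below 1.2, Grade 1 starts at 1.2.
- Over 12: the same pattern, except that a platelet count of exactly 100 is both eligible and Grade 1.

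For these four tests, an eligible child's Screening grade is therefore almost always 0. ALT is graded in multiples of the laboratory's upper limit, so the match cannot be checked. As an illustration, take a child of 12 or under with haemoglobin 8.5 at Screening, 7.5 before the injection at Month 6, and 7.5 thirty days later. Under Section 6.2 the pooled tables show a change of −1.0 and a shift from Grade 0 to Grade 1. Against the Month 6 value they show a change of 0 and Grade 1 throughout.

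**5. Which pooled outputs are reached.**
- Reached by the rule as written: laboratory change from Baseline and toxicity shift.
- Reached by default: the anti-GP split by Baseline serostatus, and the repeated ChAd3-antibody correlation figure (about 90 of the 180 children in the subset).
- Ambiguous: response, seroconversion and CMI serostatus.
- Not reached: the Day 0 randomised comparison, AE incidence, overall GMCs, out-of-range counts and the unpooled platelet percent-decrease table.

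**The case against.** The strongest reply is that Section 6.2 is only a default. The table shells govern format and content (SAP Section 8), are not among the documents, and might set a different Baseline for the pooled tables. That is possible, but the SAP text contains no such exception. Where its authors wanted pooled-specific logic they wrote it: Section 14.2.1.1 redefines the overall CMI responder by group for the pooled table. Baseline received no such sentence.

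A reader might infer that every pooled immunogenicity output uses the old value. The text does not support that. In tables re-indexed to ChAd3-EBO-Z, a pre-vaccination value can naturally mean the one before that dose, so response, seroconversion and CMI serostatus are unclear rather than wrong. Nor do the documents show how many children would change anti-GP stratum. Between Day 0 and Month 6 this group receives only Nimenrix, in areas planned to be free of Ebola transmission (Protocol Section 7).

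A reader might also infer that the primary laboratory endpoint is biased. That endpoint is the occurrence of abnormalities (Protocol Section 11.1), and out-of-range counts need no Baseline. Protocol Section 11.8 adds change from baseline as a supplement.

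Finally, the study is descriptive with no confirmatory objective. That limits the consequence, but a descriptive table should still measure change from the right point.

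**Conclusion.** The point holds for the pooled laboratory change-from-Baseline and toxicity-shift tables. Followed as written, the SAP compares the approximately 300 MENACWY-TT/EBO-Z children with a Screening value 5 to 8 months old at the ChAd3-EBO-Z dose, and mixes them in one column with children whose value is 0 to 30 days old. Abnormalities that arose before ChAd3-EBO-Z and persisted would be shown as shifts after it. By default the pooled anti-GP serostatus split and the repeated correlation figure share the fault, with a value 5 to 7 months old; the 8-month limit applies to laboratory tests only. For response, seroconversion and CMI serostatus the finding is ambiguity.

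It would be tempting to attach a bias in g/dL or platelets to this. The documents give no drift, so any such figure would be an assumption; only the factor of one half in step 3 follows from the design.

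Assumptions: planned numbers (withdrawals and Month 6 contraindications lower them), visits within the Table 6 windows, no earlier ChAd3-EBO-Z dose of the kind foreseen in Protocol Section 1.2.2.2, and no contrary rule in the table shells.

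**What to change.** Add to SAP Section 6.2: *For pooled post-ChAd3-EBO-Z outputs, Baseline, and any reference to a pre-vaccination value, is the last non-missing assessment before the ChAd3-EBO-Z dose.* This is Screening (laboratory) or Day 0 (serology, CMI) for Group EBO-Z/MENACWY-TT, and normally the Month 6 sample for Group MENACWY-TT/EBO-Z.

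- Apply it to change, grade shift, serostatus split, response and seroconversion, and the ChAd3-antibody correlation.
- Show this Baseline as the reference row of the pooled laboratory tables. No haematology or biochemistry sample is taken at Day 0, so a 0-day row built from Table 2 would hold only the Month 6 group.
- Confirm that the Month 6 blood is drawn before the injection. The protocol places both at that visit without expressly ordering them.
- Flag children whose Month 6 sample is missing, since the last non-missing value then comes from an earlier visit.

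The cost is one sentence, one derived baseline flag and a check of the table shells. The samples are already scheduled: laboratory and anti-GP in all children, ChAd3 antibody in the subset. The Day 0 tables keep their present Baseline.
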